#### 4.2.12.2 EORTC QLQ-H&N35

Time to symptom deterioration for each of the 4 symptom scales/ items in the QLQ-H&N35 (pain, swallowing, senses and speech) will be compared between treatment arms using a stratified log-rank test as described for the primary analysis of OS. The effect of MEDI4736 monotherapy vs SoC and MEDI4736 + tremelimumab combination therapy versus SoC treatment will be estimated by the HR together with its corresponding 95% CI using stratified Cox model with the same approach as described for PFS and OS analysis.

For each of these 4 symptom scales/ items in the QLQ-H&N35 above, time to deterioration in symptoms will be presented using a Kaplan-Meier plot.

A summary of the symptom improvement rate for each of the 4 symptom scales/items (pain, swallowing, senses and speech) will be produced. The symptom improvement rate for each of the 4 symptom scales/items (pain, swallowing, senses and speech) will be compared between treatment groups using a logistic regression model as described for ORR.

Summaries of absolute and change from baseline values for each of the 7 symptom scale/item (pain, swallowing, senses, speech, social eating, social contact and sexuality) and 11 single-item measures (teeth, problems with mouth opening, dry mouth, sticky saliva, coughing, feeling ill, use of analgesics, use of nutritional supplements, use of a feeding tube, weight gain, and weight loss) will be reported by visit for each treatment provided at least one treatment arm has 20 or more subjects with data at a given visit. Graphical presentations may also be produced as appropriate.

The assessment of symptoms comparing mean change from baseline using the MMRM as described for EORTC QLQ-C30 will be repeated for pain, swallowing, senses, and speech of the EORTC QLQ-H&N35. All assumptions and outputs as described for the EORTC QLQ-C30 are applicable and the same approach from EORTC QLQ-C30 will be applied.

Summary measures of overall compliance and compliance over time will be derived for the EORTC QLQ-H&N35. These will be based upon the compliance derivation described for EORTC QLQ-C30

#### 4.2.12.3 CCI [REDACTED]

CCI [REDACTED]

CCI

#### 4.2.12.4

CCI

CCI

#### 4.2.12.5

CCI

CCI

### 4.2.13 Safety

Safety data will be summarized. No formal statistical analyses are planned for safety data. All safety and tolerability data will be presented for all-comers and also for those in the PD-L1 TC/IC subgroup using the safety population. The following sections describe the planned safety summaries for AEs, vital signs, laboratory parameters, ECG and WHO/ECOG performance status. However, additional safety tables (not specified in this SAP) may need to be produced to aid interpretation of the safety data. This may include repeating the planned safety summaries for the low risk of EM subgroup. Any safety summaries examining retreatment with MEDI4736 + tremelimumab will be produced separately.

#### 4.2.13.1 Adverse Events

All AEs, both in terms of current Medical Dictionary for Regulatory Activities (MedDRA) preferred term and Common Toxicity Criteria for Adverse Events (CTCAE) grade, will be listed and summarized descriptively by count (n) and percentage (%). The current MedDRA dictionary will be used for coding. Any AE occurring before treatment with IP and which did not worsen during the course of the study will be included in the AE listings, but will not be included in the summary tables (unless otherwise stated). These will be referred to as 'pre-treatment'. However, any AE occurring before the administration of the first infusion on Study Day 1 that worsens after Study Day 1 will be regarded as treatment emergent and thus will be included in the summary tables. Note: If an AE is not worse than the baseline (pre-dose) severity then it will not be classified as TEAE.

AEs observed up until 90 days following discontinuation of IP or until the initiation of the first subsequent therapy (excluding palliative radiation as a subsequent therapy) following discontinuation of IP (whichever occurs first) regardless of whether the AE occurred during re-treatment with tremelimumab or not will be used for reporting of all of the AE summary tables. This will more accurately depict AEs attributable to IP only as opposed to presenting all AEs reported up to 90 days following discontinuation of IP. This is due to the fact that a number of AEs up to 90 days following discontinuation are likely to be attributable to subsequent therapy. However, to assess the longer term toxicity profile, a small selection of the AE summaries may be repeated containing AEs observed up until 90 days following discontinuation of IP (i.e. without taking subsequent therapy into account). A summary will also be produced containing all AEs (by system organ class and preferred term) observed from the initiation of the first subsequent therapy following discontinuation of IP until 90 days following discontinuation of IP treatment (i.e. summarizing those AEs experienced by patients taking subsequent therapy during the 90 days AE collection follow-up window post discontinuation of IP). Any data post 90 days last dose will be listed only apart from a separate summary that presents any events that occur prior to dosing or starting more than 90 days after discontinuing IP.

All reported AEs will be listed along with the date of onset, date of resolution (if AE is resolved) and investigator's assessment of severity and relationship to study drug. Frequencies and percentages of patients reporting each preferred term will be presented (i.e. multiple events per patient will not be accounted for apart from any episode level summaries which may be produced).

Summary information (the number and percent of patients by system organ class and preferred term) will be tabulated for:

- All AEs
- All AEs causally related to study medication
- AEs with CTCAE grade 3 or 4
- AEs with CTCAE grade 3 or 4, causally related to study medication
- AEs with outcome of death
- AEs with outcome of death causally related to study medication
- All SAEs
- All SAEs causally related to study medication
- AEs leading to discontinuation of study medication
- AEs leading to discontinuation of study medication, causally related to study medication

- SAEs leading to discontinuation of study medication
- SAEs leading to discontinuation of study medication, causally related to study medication
- Immune mediated AEs based on pre-defined criteria presented in the immune mediated AE charter.
- Infusion reaction AEs

An overall summary of the number and percentage of patients in each category will be presented. In addition, a truncated AE table of most common AEs, showing all events that occur in at least 5% of patients in any treatment group will be summarized by preferred term, by decreasing frequency. This cut-off may be modified after review of the data. When applying a cut-off (e.g., 5%), the raw percentage should be compared to the cut-off, no rounding should be applied first (i.e., an AE with frequency of 4.9% will not appear if a cut-off is 5%).

Each AE event rate (per 100 patient years) will also be summarized by preferred term within each system organ class. For each preferred term, the event rate (defined as the number of patients with that AE divided by the total drug exposure of patients and then multiplied by  $365.25 \times 100$  to present in terms of 100 patient years) will be presented. For the MEDI4736 + tremelimumab arm, event rates will be based upon total combination duration including any tremelimumab re-treatment period (i.e. the very last dose date of study drug (MEDI4736 or tremelimumab) regardless of it being after tremelimumab re-started should be used as last dose in the calculation)

AEs will be assigned CTCAE grades (National Cancer Institute (NCI) CTCAE version 4.03) and summaries of the number and percentage of patients will be provided by maximum reported CTCAE grade, system organ class, preferred term.

For each AE, time to first onset of the AE from the date of first dose will be presented in patients in the safety analysis.

A summary of 3 deaths tables

1. All deaths (Full analysis set)
2. Deaths within 90 days of last dose (Safety analysis set)
3. Death within 90 days of last dose or prior to start of subsequent therapy (Safety analysis set)

will be provided with number and percentage of patients, categorized as:

- Related to disease under investigation,
- AE with outcome = death,
- Both related to disease under investigation and with AE outcome=death,

- Patients with unknown reason for death and
- Other deaths.

A corresponding listing will also be produced.

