### **3.3 Safety**

Safety and tolerability will be assessed in terms of adverse events (AEs) (including serious adverse events [SAEs]), deaths, laboratory data, vital signs, electrocardiograms (ECGs) and exposure. These will be collected for all patients. Data from all cycles of treatment will be combined in the presentation of safety data. ‘On treatment’ will be defined as assessments between date of start dose and 90 days following discontinuation of IP (i.e., the last dose of MEDI4736 monotherapy, MEDI4736 + tremelimumab combination therapy, or SoC) regardless of re-treatment period. For AEs, on treatment (or treatment-emergent AEs) will be defined as any AEs that started after dosing or prior to dosing and which worsens following exposure to the treatment. If an AE is not worse than the baseline (pre-dose) severity, then it will not be classified as TEAE.

Safety analysis set will be used for reporting of safety data.

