### 3.3.2 Treatment exposure

Exposure will be defined separately for MEDI4736 monotherapy, MEDI4736 on the MEDI4736+ tremelimumab combination arm, tremelimumab on the MEDI4736+tremelimumab combination arm, and also separately for cetuximab, a platinum [carboplatin or cisplatin], and 5FU on the standard of care arm for the initial period of treatment and for the retreatment period as follows:

Total (or intended) exposure of MEDI4736 (monotherapy)

- Total (or intended) exposure is defined as the total treatment period from first dose date of study drug to earliest of “last dose date of study drug + 27 days” or death date or DCO.

Total (or intended) exposure of MEDI4736 (combination)

- Total (or intended) exposure is defined as the total treatment period from first dose date of study drug to the earliest of “last dose date of study drug + 27 days” or death date or DCO regardless of tremelimumab being re-started or not.

Total (or intended) exposure of tremelimumab (combination)

- Total (or intended) exposure is defined as the total treatment period from first dose date of study drug to the earliest of “last dose date of study drug + 27 days” or death date or DCO. This will include the sum of the duration in the 2 tremelimumab periods (i.e., initial period and re-treatment) but excluding the count of time between the 2 periods (for example, the duration would sum up to 6 months if they did 3 months in each case even if the 2 periods were separated by several months).

Actual exposure of MEDI4736/tremelimumab

- Actual exposure is defined as above, but excluding total duration of dose delays. Actual treatment duration for tremelimumab will be derived similarly as was done by total exposure, that by combining the periods of tremelimumab and summing up the delays in each period.

Total (or intended) exposure for the SOC regimens (cetuximab, a platinum [carboplatin or cisplatin], and 5FU)

- The total (or intended) exposure for the individual SOC regimens will be calculated according to the dose schedule required for each SOC regimen as follows:
  - (a) Cetuximab: Total (or intended) exposure is defined as the total treatment period from first dose date of study drug to the earliest of “last dose date of study drug + 6 days” or death date or DCO
  - (b) Platinum and 5FU: Total (or intended) exposure is defined as the total treatment period from first dose date of study drug to the earliest of “last dose date of study drug + 20 days” or death date or DCO

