The total (or intended) exposure will also be summarised by combining the SOC treatments together. The following rules will be applied for SOC total

- Total (or intended) exposure is defined as the total treatment period from first dose date of study drug to the earliest of “last dose date of YY SoC drug + xx days” or death date or DCO, xx depends on whether the patient was still receiving platinum or 5FU, or only on cetuximab:
  - if last dose of cetuximab is  $\geq 14$  days after last dose of platinum and 5FU, then YY=cetuximab and xx= 6 days
  - if last dose of cetuximab is  $< 14$  days after last dose of platinum and 5FU, then YY=platinum and xx= 20 days

Actual exposure will not be calculated for SOC.

Dose reductions are not permitted per the CSP for the immunotherapy agents (MEDI4736 or MEDI4736+tremelimumab). The actual exposure calculation makes no adjustment for any dose reductions that may have occurred.

Exposure will also be measured by the number of cycles received. For the immunotherapy arms, a cycle corresponds to a 4-week treatment; for SOC, a cycle corresponds to a 3-week treatment. If a cycle is prolonged due to toxicity, this should still be counted as one cycle. A cycle will be counted if treatment is started even if the full dose is not delivered. Each immunotherapy agent will be measured in terms of number of doses given.

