#### **Haemorrhages-related adverse events**

Treatment-emergent haemorrhage events will be identified using the Haemorrhage (excluding laboratory terms) Standardized Medical Dictionary for Regulatory Activities (MedDRA) Query (SMQ) from the current MedDRA version.

The following key summary tables and listings will be produced for the subset of patients who are reported to have a treatment-emergent adverse event within the Hemorrhage SMQ:

- Haemorrhage SMQ patient disposition (all patients)
- Haemorrhage SMQ Demographic characteristics (Safety Analysis Set)
- Haemorrhage SMQ Disease characteristics at initial diagnosis or study entry (Safety Analysis Set)
- Haemorrhage SMQ Extent of disease at study entry (Safety Analysis Set)
- Haemorrhage SMQ Adverse events in any category - patient level (Safety analysis set)
- Haemorrhage SMQ Adverse events and event rate by system organ class and preferred term (Safety analysis set)
- Haemorrhage SMQ Time to onset of adverse event (days), arranged by system organ class and preferred term (Safety analysis set)
- Haemorrhage SMQ Causally related adverse events by system organ class and preferred term (Safety analysis set)
- Haemorrhage SMQ Adverse events by system organ class, preferred term, and maximum reported CTCAE grade (Safety analysis set)
- Haemorrhage SMQ Adverse events of CTCAE grade 3 or 4 by system organ class and preferred term (Safety analysis set)
- Haemorrhage SMQ Causally related adverse events of CTCAE grade 3 or 4 by system organ class and preferred term (Safety analysis set)
- Haemorrhage SMQ All deaths (Safety Analysis Set)

- Adverse events with outcome of death, by system organ class and preferred term (Safety analysis set)
- Haemorrhage SMQ Adverse events with outcome of death, causally related to study treatment, by system organ class and preferred term (Safety analysis set)
- Haemorrhage SMQ Serious adverse events by system organ class and preferred term (Safety analysis set)
- Haemorrhage SMQ Serious adverse events, causally related to study treatment, by system organ class and preferred term (Safety analysis set)
- Haemorrhage SMQ Adverse events, leading to discontinuation of study treatment, by system organ class and preferred term (Safety analysis set)
- Haemorrhage SMQ Listing of Deaths (Safety Analysis Set)
- Haemorrhage SMQ Serious adverse events - Listing of key information (Safety analysis set)

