#### **4.2.19 Treatment exposure**

The following summaries related to MEDI4736, tremelimumab, and SoC will be produced for the safety analysis set:

- Total exposure and a plot of exposure over time (See Section 3.3.2)
- Actual exposure. (Actual exposure will not be provided for SoC patients)
- Number of dose interruptions/delays and reasons for dose interruptions/delays (drug interruptions represent interruption of an infusion and therefore any interruptions recorded on dates when study treatment was not administered will not be counted, delays are defined as a dose delay that occurs between 2 administrations of study treatment)
- RDI (entire intended treatment period).
- Cumulative exposure over time (excludes 28-day window)

Summaries of exposure will also be presented for the subgroup of discontinued patients.

All treatment information data (study drug administration, MEDI4736, tremelimumab and SoC) will be listed for the safety analysis set.

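### The AE event rate counts events for up to 90 days after last dose but divides by drug exposure that ends 27, 20 or 6 days after it, so contrasts with SoC rest on unequal mismatches

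*SAP*

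**What the plan says.** **Numerator.** SAP 4.2.13.1 sets one window: "AEs observed up until 90 days following discontinuation of IP or until the initiation of the first subsequent therapy", whichever comes first. It states that this window "will be used for reporting of all of the AE summary tables", which includes the event-rate table. SAP 3.3 makes clear that stopping IP means the last dose: "90 days following discontinuation of IP (i.e., the last dose of MEDI4736 monotherapy", and likewise for the other two arms.

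**Denominator.** The event rate is "defined as the number of patients with that AE divided by the total drug exposure of patients", rescaled to 100 patient-years. The sentence has no cross-reference. SAP 3.3.2 ends total exposure of MEDI4736 and tremelimumab at the earliest of "last dose date of study drug + 27 days", death or data cut-off. For combined SoC the same rule applies with a different tail: "xx depends on whether the patient was still receiving platinum or 5FU, or only on cetuximab". The tail is 6 days from the last cetuximab dose if that dose falls 14 or more days after platinum and 5FU, and otherwise 20 days from the last platinum dose.

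**Combination arm.** SAP 4.2.13.1 adds that the very last dose of either drug, retreatment included, counts as the last dose. This fixes the last dose but adds no follow-up time.

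**Related text.** Protocol 8.5.4 describes the optional presentation as a rate per person-years at risk. The haemorrhage section of the SAP lists "Haemorrhage SMQ Adverse events and event rate by system organ class and preferred term (Safety analysis set" and states no denominator for it.

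**The concern.** An exposure-adjusted rate is meant to let arms treated for different lengths of time be compared. That works only if each day that can supply an event also supplies person-time. Here the follow-up days after the exposure tail supply events only. The tail follows the dosing interval of the drug, so its length differs between immunotherapy and SoC by construction. Arms with the same AE risk could then show different rates because of the exposure definition alone.

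The SAP takes a different approach elsewhere. Under long-term tolerability, AE prevalence is calculated over patients on treatment or in safety follow-up, and patients without the AESI are censored at the end of safety follow-up.

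**Working it through.** The documents state no event rate, so there is no figure to reproduce. What can be checked is the length of the two periods and what follows from it.

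**Inputs.** Follow-up of 90 days (SAP 3.3, 4.2.13.1); tails of 27, 6 and 20 days (SAP 3.3.2). L is the number of days from first to last dose, which is assumed because the documents give none. Both end days are counted.

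**Periods with no death, cut-off or subsequent therapy inside 90 days**

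| | AE window | Exposure | Gap |
|---|---|---|---|
| MEDI4736 | L + 91 | L + 28 | 63 |
| SoC, cetuximab last | L + 91 | L + 7 | 84 |
| SoC, platinum rule | L + 91 | L + 21 | 70 |

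On the platinum rule the gap is 70 to 83 days, because cetuximab may run 0 to 13 days past the last platinum dose. All gaps are maxima. If subsequent therapy starts s days after last dose (s up to 90), the gap is s − 27, s − 6 or s − 20. At s = 21 that gives −6, 15 and 1 days. A negative value means exposure outlasts the AE window, because exposure does not stop at subsequent therapy.

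**Set-up A: equal AE risk and equal L.** The numerators are equal, so SoC/MEDI4736 is the inverse ratio of exposures.
- L = 112: 140/133 = 1.05 (platinum last); 140/119 = 1.18 (cetuximab last).
- L = 56: 84/77 = 1.09; 84/63 = 1.33.

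**Set-up B: equal SAP-defined exposure D.** The denominators are equal. For a rare AE with the full 90 days, and with the hazard falling to a fraction r once exposure ends, the ratio is (D + r × SoC gap)/(D + r × 63).
- D = 140, r = 1: 210/203 = 1.03 (platinum last); 224/203 = 1.10 (cetuximab last).
- D = 140, r = 0.5: 175/171.5 = 1.02; 182/171.5 = 1.06.
- D = 140, r = 0: 140/140 = 1.00 for both.
- D = 84, r = 1: 154/147 = 1.05; 168/147 = 1.14.

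**Unequal treatment time.** With L = 224 for SoC (cetuximab last), L = 112 for MEDI4736, constant hazard and the full 90 days: (315/231)/(203/140) = 0.94. SoC is now understated.

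**Monotherapy against combination.** Both use the 27-day tail, so the exposure definition builds in no difference in tail between them.

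**The case against.** The strongest objection is to the size. MEDI4736 is given every 4 weeks and cetuximab weekly, so two patients who stop on the same day have different last-dose dates. The exposure definition adds the dosing interval for that reason. On that view set-up B is the fair comparison. The ratios are then smaller and depend on the off-drug hazard, disappearing if it is zero. This stands, which is why both set-ups are shown.

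Second, reading the denominator as SAP 3.3.2 is an inference. SAP 4.2.13.1 names a total duration for the combination arm only, and SAP 4.2.19 also lists a cumulative exposure without the 28-day window. Against that, SAP 4.2.19 ties the term to that section ("Total exposure and a plot of exposure over time (See Section 3.3.2"), and SAP 3.3.2 says actual exposure will not be calculated for SoC. The inference is reasonable, but it remains one.

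Third, the consequences are bounded. SAP 4.2.13 plans no formal safety analysis, and the n (%) tables are untouched. The SAP also plans prevalence, time-to-onset, life-table and cumulative-incidence summaries for AESI groups and other important events, with the plots limited to those with at least 10 events in at least one treatment group. These give follow-up-based information where it matters most, but they do not cover every preferred term.

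Finally, patients per unit of drug exposure could be a deliberate choice, and counting only events inside the exposure period would also remove the mismatch. That would depart from the single window set for all AE tables and drop later events. A footnote alone would disclose the mismatch without removing it.

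**Conclusion.** The point holds. Followed as written, and with exposure read as SAP 3.3.2, the rate divides events from one period by person-time from another. The difference is at most 63 days per immunotherapy patient and 70 to 84 days per SoC patient. It shrinks with death, data cut-off or early subsequent therapy, and reverses if subsequent therapy starts before exposure ends.

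A reader might infer that the plan overstates SoC toxicity by 5% to 33% whatever happens off drug. The documents do not support that. Those figures need equal days from first to last dose. With equal SAP-defined exposure the illustrated ratios are 1.00 to 1.14, depending on off-drug hazard. Nor can it be said that the rate favours immunotherapy: no treatment durations are given, and the direction can reverse.

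The matter affects contrasts with SoC in descriptive tables: every preferred term and, if the same definition is used there, the haemorrhage event rate. It is worth correcting but has no bearing on the efficacy analyses.

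**What to change.** In SAP 4.2.13.1, replace drug exposure as the denominator with total time at risk over the numerator's own window. This runs from first dose to the earliest of last dose of any IP + 90 days, first subsequent therapy (palliative radiation excluded), death, withdrawal from study observation (Protocol 3.10.2) and data cut-off. Define it identically in every arm, keeping the very last dose for the combination arm. State the same denominator for the haemorrhage event rate. Leave drug exposure in the exposure tables.

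The cost is a change of SAP wording and minor reprogramming. The dates are already needed: first and last dose, death and cut-off in SAP 3.3.2, subsequent therapy in 3.2.7, and withdrawal in 3.2.9.

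The downside is that the new rates are not directly comparable with tables based on drug exposure. They average on-drug and off-drug time, so they will be lower than an on-drug rate if the hazard falls after stopping, and arms with different shares of off-drug time can still differ. In set-up B with the hazard halved and cetuximab last, the matched ratio is (182/224)/(171.5/203) = 0.96. A table note should therefore say that follow-up time is included.
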